### 11.2.2 Baseline Visit (Day 1)

Study Day 1 is per definition the day on which the first study drug infusion starts. All other Visits and Study Days are relative to the Baseline Visit. The Baseline Visit is performed at the

## Clinical Study Protocol SMOF-028-CP4 Smoflipid® (lipid injectable emulsion)

---

Investigator's clinical site.

The first study drug infusion will be started during Baseline Visit. In new home care patients it will usually be in the evening of Day 1 as these patients will stay overnight in the hospital for the first study drug infusion and leave on Day 2. Patients that have been stable on HPN prior to study participation can receive the first dose during Day 1 and leave the hospital on the same day.

Patients will be trained on handling and administration of study drug and on documentation of daily nutrition intake of all sources.

The procedures of the Baseline Visit have to be executed in the following sequence:

### A. Completion of baseline documentation

Before start of the first administration of the study drug on Day 1, all baseline documentation has to be completed (see [11.2.1 Screening Visit](#)). Furthermore, the Investigator has to confirm that all eligibility criteria are still fulfilled.

### B. Administration of Study Drug as Part of PN

If none of the exclusion criteria, and all inclusion criteria, related to the baseline documentation are met, the Investigator can proceed with the procedures of administration of the study drug.

Start of infusion of the study drug in the prescribed individual dosage with dosage titration in patients who did not receive PN before (see [Section 10.3](#)). In these patients who start PN, the initial rate of infusion of the study drug should be no more than 0.01 g fat/minute (0.05 mL/min of the study drug) for the first 10 to 15 minutes.

The study drug will be infused concomitantly with the other PN components as prescribed.

Warnings and precautions included in the Prescribing Information of both Smoflipid ([Appendix 1](#)) and Intralipid 20% ([Appendix 2](#)) will be considered before and during each administration of a Study Drug.

### C. Recording

- Recording of medication, nutrition, and adverse reactions
  - concomitant medication
  - parenteral nutrition
  - oral or enteral nutrition
  - adverse events (AEs)

## 11.2.3 Treatment Phase

During treatment phase, the patients will receive the study drug 5 to 7 times per week as part

## Clinical Study Protocol SMOF-028-CP4 Smoflipid® (lipid injectable emulsion)

---

of their PN regimen.

The frequency of Treatment Phase weekly calls is  $7 \pm 1$  days up to Day 365. In addition, monthly visits will take place at the Investigator's clinical site. The monthly site visits will be performed in a time window of  $30 \pm 5$  days.

During Treatment Phase Visits, the following procedures will be executed:

### A. Recording of therapies and adverse events

During each weekly call and each monthly visit, the following will be recorded for each study day in the interval between the last and the current visit:

- Recording of therapies and adverse reactions
  - concomitant medication
  - new AEs and outcome of formerly recorded AEs (see Section 12)
  - in home care patients: hospital readmission (date, reason)
  - in hospitalized patients: transition to home care (date)
- Recording of nutrition per study day
  - study drugs: dose prescribed, dose administered, timing
  - other PN products: dose prescribed, dose administered, timing
  - oral or enteral nutrition: products, dose prescribed, dose administered amounts and energy content; if possible, type of food and beverages,
  -

### B. Measurements and examination

The following parameters will be measured and examinations performed monthly:

- body weight, body length/height, head circumference (patients < 36 months of age)
- physical examination including Tanner stage
- vital signs: blood pressure, heart rate, body temperature

### C. Blood sampling

- Blood is sampled monthly for the following laboratory analyses (in blood, plasma or serum)
  - triglycerides
  - urea nitrogen
  - ALT
  - AST
  - direct bilirubin, total bilirubin
  - GGT
  - ALP
  - creatinine

## Clinical Study Protocol SMOF-028-CP4

### Smoflipid® (lipid injectable emulsion)

---

- electrolytes: sodium, potassium, calcium, magnesium, chloride, phosphate
- glucose
- total protein
- hematology: WBC count, RBC count, platelets count, hgb, hct
- coagulation: INR
  
- fatty acids: alpha linolenic acid, linoleic acid, arachidonic acid, docosahexaenoic acid, eicosapentaenoic acid, and Mead acid, in total plasma, and in red cell membranes.
  
- sterols:  $\beta$ -sitosterol, campesterol, stigmasterol, brassicasterol, ergosterol, cholesterol, desmosterol, lanosterol,  $\beta$ -sitostanol, lathosterol, squalene.

In case of a suspected blood stream infection CRP will be assessed in addition.

- Blood is sampled every 3 months for the assessment of
  - trace elements: ferritin, zinc, selenium, copper, manganese, chromium
  
- Blood is sampled once during the treatment phase for the following laboratory analyses:
  - In all patients genetic polymorphism of two desaturase encoding genes (FADS1 and FADS2) will be determined. The Investigator will decide the time point at which the blood sample is withdrawn.

According to the specific situation of a patient, blood samples can be drawn during the infusion of the study drug and/or other PN products (hospitalized patients with PN over 24 h/day) or between two infusions (mainly home care patients). The sampling time and the time of the last or current study drug infusion will be documented.

#### **D. Revision of dose of Study Drug and other PN components**

Dosage of the study medication and the other PN products will be checked and, if necessary adapted to changes in the clinical or metabolic condition of the patient (e.g., possible higher infusion volume as consequence of weight gain, or possible dosage reduction due to proceeding gastrointestinal adaptation).

Any changes in the prescription of the study drug or other PN products, and their reasons, will be recorded. If no changes are made, the continuation of the current dosage has to be confirmed.

Warnings and precautions included in the Prescribing Information of Smoflipid ([Appendix 1](#)) and of Intralipid 20% ([Appendix 2](#)) will be considered before the dosing of the study drug is changed or confirmed.

### **11.2.4 Final Study Visit**

The Final Study Visit will take place after cessation of the last study drug infusion. Study

---

## **Clinical Study Protocol SMOF-028-CP4**

### **Smoflipid® (lipid injectable emulsion)**

---

treatment can last up to 365 consecutive days, i.e., for one year after randomization. No patient will receive study medication beyond Study Day 366.

Up to Study Day 90, study treatment will be terminated if enteral food tolerance increases and in consequence, if less than 60% of the patient's caloric requirements are provided by PN for at least one week (see 9.4 Exclusion after Study Admission).

After Study Day 90 the study treatment will be terminated as soon as nutritional needs can be fully covered from enteral or oral nutrition or PN is continued without a lipid emulsion (i.e., PN, or at least the lipid emulsion, is no longer indicated).

The study will be terminated at any time, if infusion of the lipid emulsion cannot be continued because TG or direct bilirubin levels remain above the defined limits (cf. 10.3.4) after reduction of the study drug dosage.

During Final Study Visit, the same procedures will be executed as in the monthly Treatment Phase Visits (see above, 11.2.3). Additionally, the reason for study termination will be recorded if it takes place before Study Day 365.

**Note:** Should the Final Study Visit be performed between Day 90 and Day 365 and less than 1 week after the collection of the last blood samples, then the blood sampling will not be repeated at the Final Study Visit.

If a patient is withdrawn from the study at any time due to an AE, the patient should be followed until an outcome of the AE can be defined.

In case the study participation is terminated because of withdrawal of the informed consent, the Final Study Visit, or single procedures of this visit, will only be executed if allowed by the patient's parent(s) or legal representative(s).

If the termination occurs before Study Day 365 because of cessation of PN, and PN is restarted later, a re-treatment with study drug is not allowed.

### **11.2.5 Early Termination Visit**

There is no specific definition of an Early Termination Visit because the study can be terminated for various reasons and at any time point. Independent of the reason and the time point of termination, a Final Study Visit (see above, 11.2.4) will be performed unless it is refused by the patient's parent(s) or legal representative(s).

## **11.3 Experimental and Analytical Methods**

### **11.3.1 Anthropometric Measurements**

#### **Assessment of body weight:**

Scales used for measuring body weight of the patients must be calibrated and revised according

## Clinical Study Protocol SMOF-028-CP4 Smoflipid® (lipid injectable emulsion)

---

to applicable local requirements. The relevant documentation must be updated and available on request.

### **Assessment of body length/height:**

Body length/height of the patients will be assessed in lying/standing position with the help of a length board/stadiometer.

### **Assessment of head circumference (patients < 3 years of age):**

An accurate head circumference measurement is obtained with a non-stretchable measuring tape. The measurement should be made around the widest possible circumference of the head, i.e., over the most prominent part on the back of the head (occiput) and just above the eyebrows (supraorbital ridges).

## **11.3.2 Laboratory Variables**

Laboratory analyses will be performed in the local laboratories or in central laboratories (only fatty acids, sterols, and FADS1 and FADS2 genes).

All blood sample volumes will be specified and included in the ICFs and IRB submission documents.

### **Analyses in local laboratories**

Determination of the laboratory values will be assessed using established validated techniques at the local laboratory of the clinical site. Valid normal ranges for the age groups and certifications from all laboratories will be obtained before start of the study.

Blood samples which are drawn at home (home care patients) will be sent to the clinical site for analysis. An exact description of the methodology for drawing, handling and shipping of the samples for the analysis will be provided to the home care providers.

The Investigators will review all laboratory results. Laboratory values outside the normal range will be assessed concerning their clinical significance by the Investigator. If the out-of-range value is considered clinically significant, it will be recorded as an AE (see Section 12) and documented in the eCRF (see Section 11.4.1).

### **Analyses of fatty acids and sterols**

Analysis of fatty acids (linoleic acid,  $\alpha$ -linolenic acid, arachidonic acid, docosahexaenoic acid, eicosapentaenoic acid and Mead acid, analyzed in total plasma and in red blood cell membranes and of sterols ( $\beta$ -sitosterol, campesterol, stigmasterol, brassicasterol, ergosterol, cholesterol, desmosterol, lanosterol,  $\beta$ -sitostanol, lathosterol, squalene) in plasma will be performed at the following specialized laboratory:

██████████  
████████████████████

## Clinical Study Protocol SMOF-028-CP4 Smoflipid® (lipid injectable emulsion)

---

[REDACTED]

An exact description of the methodology for drawing, handling and shipping of the samples for the analysis of fatty acids and sterols at the central lab will be provided to the clinical sites.

Fatty acid profiles will be used for assessment of EFAD. Severity of EFAD will be graded based on triene/tetraene ratio, e.g., as suspected  $\geq 0.05$ , moderate  $\geq 0.20$  and severe  $\geq 0.40$  (Cober et al 2012).

### **Analysis of fatty acid desaturase encoding genes (FADS1 and FADS2)**

Analysis is performed only once for each patient, at the following specialized laboratory:

[REDACTED]

An exact description of the methodology for drawing, handling and shipping of the blood sample for the genetic analysis at the central lab will be provided to the clinical sites.

## **11.4 Documentation of Patient Data**

All patient data generated during the study will be documented in the patient's medical records (source data). Source data is defined as all information in original records and certified copies of original records regarding clinical findings, including observations or other activities in a clinical trial necessary for the reconstruction and evaluation of the trial.

Only the Investigator and authorized co-workers (as listed on the form "Site Delegation of Authority Log" provided by Fresenius Kabi) will transcribe patient data from the source data into the eCRF.

All evaluations reported in the eCRF must be supported by source documents.

### **11.4.1 The Electronic Case Report Form**

All patient data generated during the study will be recorded in the eCRFs provided by Fresenius Kabi/Clinipace. The eCRF is specifically designed to meet the data recording requirements of the Clinical Study Protocol and the requirements of FDA 21 CFR Part 11. Clinical Trial Data will be captured in the validated [REDACTED] system designed and tested to exceed FDA 21 CFR 11 standards, and to support the study specific protocol specifications. All completed documentation of the Operational Qualification, User Acceptance Testing, and Installation Qualification will be maintained by Clinipace. The completed project specific Data Management Plan (DMP) will further describe, in detail, how the [REDACTED] Study instance will be utilized to manage this Clinical Trial.

Only the Investigator and authorized co-workers (as listed on the form "Site Delegation of

---

## **Clinical Study Protocol SMOF-028-CP4 Smoflipid® (lipid injectable emulsion)**

---

Authority Log" provided by Fresenius Kabi and trained appropriately on the eCRF system) will complete eCRFs or make corrections to the eCRF entries, and will have access to the data or may change data, without the possibility of deleting the original entries. All study personnel involved in data entry or data review will have to adhere to the eCRF completion guidelines. After completion, each eCRF will be electronically signed and dated by the Investigator.

For all laboratory data, the units or any transformation of units must be clearly defined. Transformation of data during the data processing will be documented.

This study will be monitored regularly by a CRA from Clinipace. The CRA will check for completion of the entries in the eCRFs, their compliance with the study protocol and with GCP, and will compare the eCRF entries with the source data. Source data verification will be performed for all patients and 100% of the data. A 100% accuracy and completeness check will be performed on the ICFs. A detailed list of all monitoring activities to be performed during the study will be included in the Monitoring Manual (see Section 13).

## **12. Adverse Events and Serious Adverse Events**

### **12.1 Definitions**

#### **12.1.1 Adverse Event (Adverse Experience, AE)**

Adverse event (AE) means any untoward medical occurrence in a patient administered a pharmaceutical/medicinal product and which does not necessarily have to have a causal relationship with this treatment. An AE can therefore be any unfavourable and unintended sign (e.g., an abnormal laboratory finding), symptom, or disease temporally associated with the use of a pharmaceutical/ medicinal product, whether or not considered related to the pharmaceutical/medicinal product.

An AE may be:

- A new illness
- Worsening of a sign or symptom of the condition under treatment or of a concomitant (pre-existing) illness
- An effect of the study medication
- An effect of a comparator drug
- Unrelated to participation in the clinical study
- A combination of such factors

#### **12.1.2 Adverse Drug Reaction (Adverse Reaction, ADR)**

For marketed products, all noxious and unintended responses to a pharmaceutical/medicinal product related to doses normally used in human for prophylaxis, diagnosis, or therapy of disease or for modification of physiological functions should be considered as Adverse Drug

Reactions.

### **12.1.3 Serious Adverse Event (SAE) or Serious Adverse Reaction (SAR)**

An SAE or SAR is any untoward medical occurrence (effect, reaction) that at any dose:

- Results in death
- Is life-threatening\*
- Requires inpatient hospitalization or prolongation of existing hospitalization
- Results in persistent or significant disability/incapacity
- Is a congenital anomaly/birth defect
- Is of medical importance\*\*

\* The term “life-threatening” in the definition of “serious” refers to an event in which the patient was at risk of death at the time of the event; it does not refer to an event which hypothetically might have caused death if it were more severe.

\*\* Important medical events that may not be immediately life-threatening or result in death or hospitalization, but may jeopardize the patient and may require intervention to prevent one of the other outcomes listed in the definition above, should also be considered as serious. Important medical events should also usually be considered serious (21 CFR 312.32(a)).

Events that do not fit in any of the above categories are to be considered non-serious AEs or non-serious ADRs.

#### **12.1.3.1 Suspected Adverse Reaction**

Suspected adverse reaction means any AE for which there is a reasonable possibility that the drug caused the AE. For the purposes of IND safety reporting, ‘reasonable possibility’ means there is evidence to suggest a causal relationship between the drug and the AE. A suspected adverse reaction implies a lesser degree of certainty about causality than adverse reaction, which means any AE caused by a drug (21 CFR 312.32(a)).

#### **12.1.4 Unexpected (Serious) Adverse Reaction**

An Unexpected (Serious) Adverse Reaction is a reaction, where the nature or severity or outcome is not consistent with the applicable reference safety information. Reports which add significant information on the specificity, increase of occurrence, or severity of a known, already documented (serious) adverse reaction constitute unexpected events.

The reference safety information for assessment of expectedness is the current version of the Prescribing Information for Smoflipid ([Appendix 1](#)) and Intralipid 20% ([Appendix 2](#)).

#### **12.1.5 Suspected Unexpected Serious Adverse Reaction (SUSAR)**

Suspected unexpected serious adverse reactions (SUSARs) are all ADRs that are considered to be both:

- Serious, and

## Clinical Study Protocol SMOF-028-CP4 Smoflipid® (lipid injectable emulsion)

---

- Unexpected

### 12.2 Assessment of Adverse Events

For each AE, the Investigator will assess:

- Seriousness (as defined in section 12.1.3)
- Intensity/Severity
- Causality (to study drugs and study procedures)
- Outcome
- Action taken

#### 12.2.1 Intensity/Severity

For the intensity/severity assessment of AEs based on clinical signs and symptoms, abnormal laboratory parameters or vital signs, the "Common Terminology Criteria for Adverse Events" (CTCAE) V4.03, should be used as far as reasonable (see [Appendix 3](#)). The Common Terminology Criteria for AEs is a descriptive terminology which can be utilized for AE reporting. A grading (severity) scale is provided for each AE term.

If these criteria are not reasonably applicable to an AE, the event's intensity/severity should be classified according to the Investigator's discretion as close as possible to CTCAE V4.03 based on the comparison with the most severe case encountered in past training and clinical experience. For such events the following general category descriptions may be used ([Table 2](#)).

**Table 2: Intensity/Severity Definitions for Adverse Events and Serious Adverse Events**

Grade	Category	Definition/Explanation
1	Mild	Asymptomatic or mild symptoms; clinical or diagnostic observations only; intervention not indicated.
2	Moderate	Minimal, local or non-invasive intervention indicated; limiting age-appropriate instrumental activities of daily living.
3	Severe	Severe or medically significant but not immediately life-threatening; hospitalization or prolongation of hospitalization indicated; disabling; limiting self care activities of daily living.
4	Life-Threatening/Disabling*	Life-threatening consequences; urgent intervention indicated.
5	Fatal**	Death related to the AE.

\*Life-threatening/disabling or \*\*fatal AEs will also meet the identical seriousness criteria and

thus will qualify as SAEs.

### **12.2.2 Causality/Relationship to Study Drug**

For all AEs, the causal relationship to study drug and to study procedures is to be assessed by the Investigator (regardless of whether they occurred under investigational drug or control drug).

#### **Related:**

A causal relationship between a drug and an AE can be assumed if there is at least a reasonable possibility for such a causal relationship. The expression “reasonable possibility” is meant to convey in general that there are facts (evidence) or arguments to suggest a causal relationship. A causally related AE is equal to an ADR.

#### **Not related:**

Not related with the use of a drug means that the criteria mentioned above are not met, or that a causal relationship is ruled out.

Each causality assessment should be substantiated by the Investigator; in case of “not related” at least one (e.g. the most probable) alternative cause should be provided with the assessment.

### **12.2.3 Relationship to Study Procedures**

Relationship to Study Procedures means that there is a reasonable possibility that the event is caused by specific circumstances of the protocol such as diagnostic or administration procedures.

### **12.2.4 Outcome**

The outcome of the AE (and NOT the patient’s outcome) is to be assessed at the time of documentation of the AE based on the following categories:

1. Resolved (i.e., complete resolution of AE)
2. Resolved with sequelae
3. Not resolved (includes AEs which are improving but not yet resolved completely, AEs which are ongoing at time of documentation, and AEs which are still present when a patient dies due to other causes or due to another AE).
4. Fatal (= death due to the AE).
5. Unknown (e.g., if patient is lost to follow-up).

### **12.2.5 Action Taken**

The action taken to study drugs by the Investigator as a result of the AE will be classified in one of the following categories:

1. None (= continuing according to protocol)

## Clinical Study Protocol SMOF-028-CP4 Smoflipid® (lipid injectable emulsion)

---

2. Dose reduced; this could mean:
  - a) Reducing the dose of the study drug
  - b) Maintaining the dose level, despite required increase as per protocol
  - c) Reducing the frequency of administration
3. Study drug discontinued and restarted
4. Study drug discontinued permanently

In addition, the Investigator needs to provide information on other therapy or countermeasures, such as:

- a) Drug therapy was initiated to counteract the AE
- b) Dose of concomitant medication was changed
- c) Non-drug remedial therapy was initiated

If considered necessary, the Investigator may decide to withdraw patients from the study as a consequence of AEs.

### 12.3 Reporting and Documentation Procedures

In this study, all AEs – except AEs based on abnormal laboratory parameters or vital signs with an intensity/severity grade 1 (see Table 2) that has no clinical relevance – have to be documented and reported.

If the same AE occurs frequently during the study and all episodes have the same main AE characteristics (intensity, causal relationship, outcome), this should be documented as one AE with multiple episodes.

All other AEs, including those known to be associated with the study drugs, are to be completely documented and reported.

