According to the Smoflipid Prescribing Information ([Appendix 1](#)), the adverse reactions in > 1% of 229 patients treated in clinical studies with Smoflipid were nausea (9%), vomiting (7%), hyperglycemia (5%), flatulence, pyrexia, abdominal pain (4% each), increased blood triglycerides, hypertension (3% each), sepsis, dyspepsia, urinary tract infection, anemia, and device related infection (2% each). Furthermore, the components of Smoflipid may cause hypersensitivity reactions. Parenterally administered lipid emulsions are an independent risk factor for the development of catheter-related bloodstream infections.

According to the Prescribing Information of the standard-of-care emulsion Intralipid 20%

---

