## Clinical Study Protocol SMOF-028-CP4 Smoflipid® (lipid injectable emulsion)

**Table 3: Documentation of AEs (Laboratory parameters and vital signs)**

Severity Grade*	Clinically relevant	Documentation as
1	Yes	AE in eCRF
	No	No documentation necessary
2	Yes/No	AE in eCRF
3	Yes (typical)	AE in eCRF; if serious, additionally on SAE report form
4	Yes	AE in eCRF; additionally on SAE report form
5	Yes	AE in eCRF; additionally on SAE report form

\*According to CTCAE V4.03 ([Appendix 3](#)) as far as possible

If a patient is withdrawn due to an AE at the end of the study treatment period, the patient should be followed-up until an outcome of the event can be defined. If this is not possible due to clinical or organizational reasons, an outcome assessment has to be performed by the Investigator. A final examination should be performed.

AEs are generally coded according to Medical Dictionary for Regulatory Affairs (MedDRA). At the end of the study before the clinical data base is closed, all AEs will be re-coded according to the latest MedDRA version available.

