### 12.3.2 Reporting of Serious Adverse Events

The Investigator should not delay initial SAE report entry due to missing data. As soon as the minimum information is available the initial SAE report will be entered into the eCRF, in any case, no later than 24h after becoming aware of the SAE. The eCRF will automatically generate a notification e-mail that will inform the safety associate at Clinipace and the Director Global Safety at Fresenius Kabi that an SAE has been reported.

Each initial SAE report should contain at least the following information:

- Study number
- Patient number
- Patient's date of birth (or age)
- Investigator's name and address
- AE (description, start date, outcome on the day of the report)
- Investigator's assessment of seriousness and intensity/severity
- Investigator's assessment of causal relationship to study drug and study procedures
- Action taken to the study drug

If necessary, the Investigator will provide follow-up reports immediately after knowledge of further relevant information.

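### The rule for merging repeat adverse event episodes leaves out seriousness and action taken, so a merged record may not be classifiable on either

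*Combined protocol and SAP*

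**What the plan says.** Section 12.2 has the Investigator judge five things for each AE: seriousness, intensity, causality, outcome and action taken. Under Section 12.2.5, "The action taken to study drugs by the Investigator as a result of the AE will be classified in one of the following categories", and the categories run from none to permanent discontinuation.

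Section 12.3 then sets the merging rule. Its trigger is "If the same AE occurs frequently during the study", with no number or interval attached. Its condition and consequence are that "all episodes have the same main AE characteristics (intensity, causal relationship, outcome), this should be documented as one AE with multiple episodes". Soon afterwards the section requires complete documentation of all other AEs. That sentence may exempt merged episodes. It may equally refer back to the section's earlier exception for grade 1 laboratory and vital-sign findings.

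Section 12.3.2 runs a separate route for SAEs, with an initial report due "no later than 24h after becoming aware of the SAE". Section 7.2.3 plans descriptive counts and percentages and leaves methods to a SAP whose text is not in the material reviewed.

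**The concern.** The condition for merging is narrower than the list of attributes that the record has to carry. Episodes that agree on the three tested attributes may still differ on the other two. The merged record then has to give one answer on seriousness and one on action taken for episodes that had different answers.

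Safety is half of the study objective (Section 5) and all AEs are a safety variable (Section 5.2). Treatment runs from 90 to 365 days, long enough for events to recur. Section 4.3 names one that plausibly could: "Parenterally administered lipid emulsions are an independent risk factor for the development of catheter-related bloodstream infections". At stake are the seriousness and action-taken classifications in AE tables and, if those tables count records, the number of events. Episode detail that is not collected during the study may be hard to recover after database lock.

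**Working it through.** The plan states no figure on this point, so the check is mainly a comparison of text.

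**1. Attributes assessed against attributes tested**

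| Assessed for each AE (12.2) | Tested before merging (12.3) | Fixed by the tested attributes? |
|---|---|---|
| Intensity | Yes | n/a |
| Causality | Yes | n/a |
| Outcome | Yes | n/a |
| Seriousness | No | Only at grades 4 and 5 |
| Action taken | No | No |

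The footnote to Table 2 makes life-threatening/disabling and fatal events serious, so equal intensity settles seriousness at grades 4 and 5. Below that it does not, because Section 12.1.3 defines seriousness by consequences such as inpatient admission. Table 3 confirms the separation for laboratory and vital-sign AEs, where a grade 3 finding is "AE in eCRF; if serious, additionally on SAE report form".

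**2. A case that the rule lets through**

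Take a patient with frequent grade 3 episodes of one event, all judged not related and all resolved. One episode leads to admission and to study drug being stopped and restarted. The others lead to neither. All three tested attributes agree, so the rule calls for one record. Seriousness is yes for one episode and no for the rest. Action taken is discontinued-and-restarted for one and none for the rest. Whichever single value is entered is wrong for at least one episode. This step needs no assumed rate.

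**3. Whether another section repairs it**

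- Section 12.3.1 sends all AEs to the AE page of the eCRF. It does not ask for the number, dates, seriousness or action of each merged episode.
- Section 12.3.2 requires start date, seriousness and action in each initial SAE report. That covers serious episodes in the SAE report but leaves the AE record unresolved.
- Section 7.2.3 does not say whether AE tables count patients, records or episodes.

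**4. Illustration of the count effect (assumed rates)**

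Inputs from the protocol: 24 patients per arm in each of three age groups, so 3 × 24 = 72 per arm (Section 7.2.1), and 90 to 365 days of treatment (Section 6.1). Assumed: 0.25, 1 or 3 episodes per patient-year, Poisson occurrence, the same follow-up for all patients, every repeat merged, and tables that count records. With m the mean number of episodes per patient:

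- episodes = 72m
- records = 72(1 − e^−m)
- share lost = 1 − (1 − e^−m)/m

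| Assumed rate per year | 365 days: episodes → records (lost) | 90 days: episodes → records (lost) |
|---|---|---|
| 0.25 | 18.0 → 15.9 (12%) | 4.4 → 4.3 (3%) |
| 1 | 72.0 → 45.5 (37%) | 17.8 → 15.7 (11%) |
| 3 | 216.0 → 68.4 (68%) | 53.3 → 37.6 (29%) |

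If the other arm had half the rate, the ratio of record counts would be (1 − e^(−m/2))/(1 − e^−m). At 365 days that is 0.53, 0.62 and 0.82 for the three rates, against a true 0.50.

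Each entry is a ceiling at its assumed rate, because it ignores both the *frequently* trigger and the matching condition. The number of patients with at least one event is 72(1− e^−m) with or without merging, so patient-level incidence loses nothing.

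**The case against.** A reader might infer that recurrent risks, catheter bloodstream infection above all, are being under-counted. The documents do not support that:

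- The rule applies only to events that occur frequently, and it describes the result as one AE with several episodes. Multiplicity is therefore acknowledged, and the eCRF, which was not supplied, may hold episode dates.
- Leaving out two attributes misclassifies episodes within a record. Any loss of counts comes from merging itself and would largely remain if both attributes were added to the rule.
- Nothing in the documents says that catheter infections are frequent or uniform on the three attributes. They are not a separate target variable. Table 3 does not govern them, since it is limited to laboratory parameters and vital signs.
- A reader might also infer that a later serious episode escapes its own report. Section 12.3 does not suspend the 24-hour duty.
- Other records help with reconstruction: readmission dates and reasons for home care patients and study-drug doses for each study day (Section 11.2.3), and concomitant medication with dates and indication (Section 10.8).
- No event-rate analysis is specified and the study is descriptive and unpowered, so a rate comparison between arms is a reviewer's preference.

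These points stand, and they limit the finding. They do not remove the conflict between Sections 12.2 and 12.3. It could be argued that the bracketed list is only illustrative, but it is not worded as examples. Reconstruction from other records is also no substitute for a correct AE record.

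**Conclusion.** The point holds as a flaw in a stated rule. As written, Section 12.3 permits one AE record to combine serious with non-serious episodes, or episodes with different study-drug actions. Such a record cannot be classified correctly for seriousness or action taken. This rests on the text alone.

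Understatement of event-level counts is a conditional risk. It needs tables that count records, and it arises because neither the number nor the dates of merged episodes are required. Its size cannot be derived from the documents, and the percentages in the illustration are not findings about this trial.

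This is a cheap improvement to the protocol wording and does not threaten the study's main results.

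**What to change.** In Section 12.3, allow merging only for episodes that are non-serious, led to no action on study drug, and match on intensity, causality and outcome. Require the number of episodes and the start and stop date of each. Document every serious episode, and every episode leading to a study-drug change, as its own AE record.

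In Section 12.3.2, state that each serious episode is a new SAE with its own 24-hour report. It would also help to define *frequently*, and to state in the SAP whether AE tables count patients, records or episodes.

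The cost is a few sentences in the protocol and the eCRF completion guidelines, and a few more AE entries per site.
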